Participants will be tracked in REDCap in order to maximize retention in the study and, as necessary, to capture any drop-outs or withdrawals that occur during the study period. PLAN coaches can verify the status of their FBT families by accessing the REDCap Record Status Dashboard, which will list all existing records/responses and their status (i.e., incomplete or complete) for every data collection instrument in the study. PLAN coaches can verify that FBT families and UC families at their site have completed assessment time points as well as the family members that participated in these assessments. Additionally, PLAN coaches can utilize the REDCap calendar to manage participants and appointments, and they will complete Tracking Forms each week to document session attendance or absence of their FBT families. In order to ensure that families in both arms are captured at all necessary time points, the DCC will send regular reports to indicate participant status and subsequent required actions on behalf of the study team.

5. Participant Withdrawal or Termination

Children and parents can withdraw from the research at any time, and siblings and non-participating parents can withdraw or be withdrawn without any consequences to the other family members’ status in the study. If participants withdraw, they will be debriefed about the nature of the study, asked permission to obtain data collection through medical records or brief appointments, and, if terminated, provided with the reason for their removal as well as a referral if deemed appropriate. Any information that had been provided may be retained by the researcher and analyzed. This includes permission to collect body composition information from their physicians at determined measurement time points (if not revoked upon their withdrawal).

Participants who exhibit unhealthy weight loss, clinically concerning symptoms of disordered eating, or develop an illness or condition that would bias the data may be withdrawn from research analyses, as determined by the SEC, SMC, and the Data Safety and Monitoring board (see **section IX**) and referred to an appropriate professional (*This change was made on 3.23.18 prior to review and approval by the DSMB, DSMB approved protocol addenda on 11.2.18*).

Lost to Follow-Up for FBT Families (DSMB approved protocol addenda, 9.29.19): A designation of Lost to Follow-Up (LTF) is applied to intervention families that we have not had contact with for 3 months (90 Days).

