2. Adequacy of Protection Against Risks

All key personnel involved in the design or conduct of research involving human subjects will receive the required education on the protection of human research participants prior to the start of the study. The PLAN coaches will collect and manage data collected from these participants and will not engage the pediatricians in the research. If required by a site's individual IRB, PLAN coaches will complete Business Associate Agreements prior to their work within the practices.

Individuals administering assessments will be made aware of the possibility of a participant's discomfort about answering questions or having height and weight measured. Participants will be informed that they do not have to answer any questions that make them uncomfortable, and height and weight will be measured in private to minimize embarrassment. Participants will be advised of the possibility of hunger with dieting or soreness after exercise. In order to reduce the risk of exercise-related injury, all participants will be encouraged to follow their primary care physician's instructions regarding exercise.

On an ongoing basis, the family meetings will serve as the primary venue to detect and address any eating disturbance, and study PLAN coaches will be trained to monitor, recognize, and intervene if symptoms of disordered eating behaviors or attitudes emerge. If a PLAN coach notices that a participant is consuming a nutritionally inappropriate quantity or quality of foods, he or she will assist the participant in achieving appropriate intake. Should a participant show symptoms consistent with an eating disorder during treatment, the PLAN coach, in consultation with the treatment supervisor at the Training and Fidelity Core, will decide whether to recommend that the family be withdrawn from treatment and/or refer them for treatment elsewhere. This will be stated in the consent form.

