To account for differences in the frequency of participant contact between the two study groups, blinded measurement staff will systematically assess for AEs in both the intervention and control groups through use of a standardized questionnaire (see MOP) that is administered at each major assessment time point. If any items are endorsed on the questionnaire, the blinded measurement staff will gather additional information and, if necessary, follow the steps for recording and reporting adverse events outlined below and in section **IX.E**. AEs uncovered in the course of treatment will also be subject to the procedures below. Combining between visit and at visit AEs will result in an alternative count that the DSMB requested. This alternative count will be comprised of all AEs, whether reported at or between visits. Blinded coaches will be unaware if an AE was reported between visits, and any duplicates will be removed by an unblinded reviewer (*DSMB Approval, 12.16.2020*)

All AEs, including those not meeting the criteria for SAEs, will be captured on an Adverse Event Form or Serious Adverse Event Form (see **Appendix D**), which must be approved of and signed by the clinical site PI. Information to be collected includes event description, time of onset (and offset if applicable), assessment of severity, relationship to study treatment, expectedness, actions taken,

and outcome of the event. Additionally, all SAEs will require categorization (e.g., death, hospitalization, permanent impairment, etc.) and documentation of any interventions implemented in response to the event.

All AEs occurring during a participant's study participation must be documented appropriately regardless of relationship. All AEs will be followed by the DSMB to adequate resolution and will be recorded in the data collection system. Any medical condition that is present at the time that the participant is screened will be considered as baseline and not reported as an AE. However, if the study participant's condition deteriorates at any time during the study, it will be recorded as an AE. Changes in the severity of an AE will be documented to allow for an assessment of the duration of the event at each level of severity. AEs characterized as intermittent require documentation of onset and duration of each episode.

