The DCC will organize annual site visits to all clinics that will focus on a detailed review of study procedures. Special additional site visits may occur if routine quality control measures determine that a clinic is having difficulty with some aspect of the protocol. Site visitors will prepare an agenda that will include observations of the performance of study procedures and of the filing system that is used to store completed data forms. They will confirm that data forms are correctly filed, that IRB approvals are available, and that changes on forms are appropriately initialed and dated by the person who made the changes. In addition, site visitors may do random data audits in accordance with section **X.F.2**. Site visits will generally be conducted by a DCC staff person and by an investigator from another clinic.

III. Statistical Considerations

A. Statistical Analysis Plan

Data will be analyzed with SAS using the intention-to-treat principle. P-values less than 0.05 will be considered significant and all tests are two-sided. Details of how the intention-to-treat principle will be implemented are contained in a later section.

B. Primary Analysis

The primary goal of this study is to determine whether the change in weight status among children who have overweight/obesity (*Primary Specific Aim 1, DSMB approved protocol addenda, 11.2.18*) is superior among those who are randomized to family-based treatment (FBT) as compared to those who are randomized to usual care (UC) when treated in a primary care setting. The primary outcome measure in children is the percent over the age- and sex-specific 50th BMI percentile. The specific question of interest in the primary analysis is whether the change from baseline to 24 months in the intervention group is greater in the FBT group than in the UC group.

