The primary analysis will be an intention-to-treat analysis of the child that includes all subjects. Recalling that the primary analysis involves an analysis of covariance with the 24-month value of percent over BMI (the primary outcome measure) as the dependent variable, the inclusion of all subjects will reflect the following three considerations.

1. If the 24-month value of the primary outcome is available, the child will be included in the primary analysis without the need for further considerations.
2. If the 24-month value of height and/or weight (the defining components of the primary outcome) is missing and the child had height and weight data collected by his or her pediatrician at a clinic visit that occurred within 30 days of the targeted 24-month PLAN assessment, the following considerations will be used in imputing the 24-month value to be used in the primary analysis. Those considerations are designed to account for the anticipated imprecision of values measured at the pediatrician's office.
 - a. Within each clinic, a regression model that will allow us to impute 24-month values will be generated. Using all PLAN children who attend a particular clinic and who have both precisely measured PLAN height and weight data and less precise height and weight data measured at the clinic within 30 days of the PLAN measurement, clinic-specific regression models will separately predict the true height and weight using the age and sex of the subject as well as the height and weight value measured at the clinic. The goal will be to perform these calculations on a clinic-specific basis because the causes and magnitude of measurement error may differ

from clinic to clinic. However, if the number of subjects at a clinic who have the requisite height and weight data is less than 15 (less than 5 times the number of predictors), we will use all data from all clinics at the relevant study site to perform the desired imputation.

- b. Recalling that the children of interest in this scenario have clinic data collected within 30 days of the targeted 24-month PLAN assessment, the clinic-specific height and weight value calculated above will be used to impute the PLAN 24 month values from the contemporaneous value measured at the clinic. This imputed value will be used in the primary analysis.

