3. A per protocol dataset will be defined as including all subjects who attend at least 80% of the prescribed sessions. Sensitivity analyses will assess whether applying the primary analysis to the per protocol dataset yields the same result as the primary ITT analysis. *All control group subjects who do not drop out of the study will be considered to be part of the per protocol dataset. We recognize that this implies a somewhat different definition in the two study arms. But we do not consider this to be a problem since this is a sensitivity analysis whose goal is to repeat the primary analysis in a different setting (DSMB approved protocol addenda, 11.2.18).*
4. Random coefficient models that potentially use different covariance structures in the two study arms will include all primary outcome data collected at baseline, 6, 12, 18, and 24 months. Since weight change often occurs at a more rapid rate early in a weight loss study, these sensitivity analyses will include an exploration of non-linear possibilities such as quadratic models. They will also assess contrasts that compare changes from baseline to 24 months across groups in order to use an alternative model for testing the central hypothesis of the primary analysis.
5. Repeat the primary analysis after adjusting for baseline covariates. The covariates to be used are the race and sex of the participating child, family income, the educational level of the participating parent, and whether there are one or two parents in the household.

F. The Time Between Randomization and the Measurement of the Primary Outcome

The time between randomization and the measurement of the primary outcome will vary among participants and will potentially differ between groups. Our approach to addressing the potential impact of this reality is described below.

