The DCC will use the REDCap randomization module to create an online password protected randomization system that will facilitate the random assignment of families. When the website is entered, the user will provide information that establishes the eligibility of the family. Group assignments will be revealed only if all eligibility criteria are satisfied. To avoid temporal bias, randomization will be blocked within clinic using random block sizes in order to preclude the possibility that investigators might know in advance the assignment of the last family in a particular block.

2. Standardization of Height and Weight Measurements

Verifications for collecting and entering the data for the height and weights will be followed to decrease bias. All stadiometers and scales used will be calibrated and consistent between all sites. PLAN coaches and assessors will be trained and tested on protocols for obtaining these measures. All weight measurements will be taken according to a uniform protocol and written on hard copy measurement sheets. The handwritten weights will be manually entered into the REDCap database by a blinded measurement coach, which will eliminate potential measurement bias and minimize errors in data entry (*DSMB approved change, 11.18.19*). Both the written record and the measure in REDCap will be verified. *Hard copy height and weight measurement forms will be uploaded to the secure REDCap database to allow the CCC, DCC and TFC to check for transcription and/or unit of measurement errors.* Any malfunctions of equipment will be reported to the study staff to resolve immediately. Any measurements outside of the range of normal will be flagged in REDCap and staff notified to retake measurements.

3. Masking Procedures

Masking refers to no knowledge regarding treatment assignment. It is not the same as concealment, which refers to random assignment to groups. Treatment masking represents an extension of concealment, to minimize bias in how participants assigned to different groups are treated. In the current study, the research assistants and coaches who are doing the measurements will be blinded, or masked as to treatment assignment, and the PIs for the Clinical Coordinating Center and Training and Fidelity Cores (Drs. [name] and [name]) and the DSMB will be masked as to treatment assignment. However, it is impossible to mask families, the family's PLAN coach, or pediatricians to group assignment. Families and PLAN coaches will

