1. Strongly Agree
2. Agree
3. Neither Agree or Disagree
4. Disagree
5. Strongly Disagree

The content of FBT is clear.

1. Strongly Agree
2. Agree
3. Neither Agree or Disagree

4. Disagree
5. Strongly Disagree

FBT can be implemented without requiring an extensive training.

1. Strongly Agree
2. Agree
3. Neither Agree or Disagree
4. Disagree
5. Strongly Disagree

FBT can be adapted or modified to suit the needs of the interventionist.

1. Strongly Agree
2. Agree
3. Neither Agree or Disagree
4. Disagree
5. Strongly Disagree

The benefits of using FBT with my clients are obvious/visible.

1. Strongly Agree
2. Agree
3. Neither Agree or Disagree
4. Disagree
5. Strongly Disagree

The evidence regarding the impact of FBT is available.

1. Strongly Agree
2. Agree
3. Neither Agree or Disagree
4. Disagree
5. Strongly Disagree

The content of FBT is relevant to my work as a clinical treatment provider.

1. Strongly Agree
2. Agree
3. Neither Agree or Disagree
4. Disagree
5. Strongly Disagree

Coach consent

Please upload the .pdf file of the signed Coach consent.

Indicate yes or no that Coach consent is uploaded.

[figure not shown]
- No

- Yes

Why is the coach consent not uploaded? _____

D. Additional Forms

Figure 1. Study Flow Chart

PLAN Adverse Event Questionnaire

During the time since your last visit on (*insert date of last major assessment*), have you or your child:

1. Been hospitalized overnight?

YES NO

2. Been to the emergency room or an urgent care clinic?

YES NO

3. Been treated by a medical provider for illness or injury?

YES NO

4. Had any injuries (e.g., sprained ankle or broken bone)?

YES NO

5. Started any new medications or receive a change in dosage of a current medication?

YES NO

6. Experience increased symptoms of a current illness or injury (If applicable)?

YES NO

7. Seen a new counselor, psychologist, or psychiatrist?

YES NO

8. Gone long periods (8 waking hours or more) without eating to control your weight?

YES NO

9. Felt like you have lost control over your eating?

YES NO

10. Thrown up after eating?

YES NO

11. Taken laxatives or diet pills?

YES NO

12. Felt particularly nervous, worried, or anxious?

YES NO

13. Felt very sad or down? Or lost interest in things that you normally enjoy doing?

YES NO

(This change was made on 5.23.18 prior to review and approval by the DSMB, DSMB approved protocol addenda on 11.2.18)

ADVERSE EVENT FORM

The Effectiveness of Family-based Weight Loss Treatment Implemented in Primary Care

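### The withdrawal clause lets index children be dropped from analysis for post-randomisation events and is not reconciled with the intention-to-treat primary analysis

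*Combined protocol and SAP*

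**What the plan says.** The exclusion clause is in the protocol section on Participant Retention, item 5 (Participant Withdrawal or Termination). Its triggers are unhealthy weight loss, clinically concerning signs of disordered eating, and a third, open category: those who "develop an illness or condition that would bias the data may be withdrawn from research analyses". The decision lies with the Study Executive Committee (SEC), the Safety Monitoring Committee (SMC) and the DSMB. The clause points to the safety section, which gives no weight-loss or illness threshold and no rule for removing anyone from an analysis.

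The Statistical Considerations say otherwise. Section A states: "Data will be analyzed with SAS using the intention-to-treat principle". Section B.7 states: "The primary analysis will be an intention-to-treat analysis of the child that includes all subjects", then gives three routes to a 24-month value: a study measurement, a clinic-based value, or multiple imputation. It makes no exception for children removed under the withdrawal clause.

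Section E lists five sensitivity analyses. Two concern who provided follow-up data. One is per protocol: "A per protocol dataset will be defined as including all subjects who attend at least 80% of the prescribed sessions", with usual-care (UC) children counted if they did not drop out. The other two are a longitudinal model and a covariate adjustment. None uses the withdrawal triggers.

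**The concern.** Two operative texts conflict and neither refers to the other. Any use of the clause on an index child in the primary analysis would mean that not all randomised children are analysed.

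The triggers make this more than a formality. Unhealthy weight loss is close to an extreme value of the primary outcome. The protocol's own risk section says that attention to dieting may lead to an eating disorder in some children, and Table 8 lists new eating disorders as expected and possibly related. Excluding on such events conditions on something treatment may have caused.

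Detection is also likely to differ by arm. FBT children are weighed at every session, and for eating problems "the family meetings will serve as the primary venue to detect and address any eating disturbance". UC children have no such meetings. The adverse event section recognises the imbalance: "To account for differences in the frequency of participant contact between the two study groups, blinded measurement staff will systematically assess for AEs". That questionnaire goes to both arms and covers fasting ("Gone long periods (8 waking hours or more) without eating to control your weight"), loss of control over eating, vomiting, and laxatives or diet pills. With the six-monthly weights in both arms, it narrows the gap without closing it.

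The efficacy comparison is what is at stake. Adverse event reporting is not affected.

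**Working it through.** **The texts side by side.** Could the clause mean only that treatment stops? The protocol words that differently: Adequacy of Protection Against Risks speaks of withdrawal from treatment when eating-disorder symptoms appear. The retention clause speaks of analyses. Could it apply only to a secondary or sensitivity analysis? It names none, and none of the five in section E uses its triggers. Section B.8 plans sensitivity analyses for outlying values, also without these triggers.

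**Inputs from the documents.** 528 families allocated 50/50, so 264 per arm; planning difference 5.3; SD 15.3 or 12.7; UC change SD 10.08; two-sided alpha 0.05; 12 FBT coaches (3 at each of 4 sites), so 22 families each. Table 1 gives power 0.84 at N=528, FBT ICC 0.04, SD 15.3, difference 5.3.

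**Assumptions, because the documents give no rate.** A share p = 1%, 2% or 3% of FBT children is removed (2.6, 5.3 or 7.9 of 264; about 3, 5 or 8).

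**Reproducing the plan's figure.** SE² = 15.3²/264 × [(1 + 21 × 0.04) + 1], so SE = 1.59. With a noncentral t on 12 − 4 = 8 df, power is 0.832 against the stated 0.84. This form falls within 0.02 of the table in 15 of 16 cells checked at N=528, with a largest gap of 0.021.

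**Shift in the FBT mean.** For a normal outcome with one tail removed, shift = r × SD × φ(z)/(1 − p), where z is the upper p quantile and r is the correlation of the trigger with 24-month change. The factor φ(z)/(1 − p) is 0.0269, 0.0494 and 0.0701 for the three values of p.

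| Case | 1% | 2% | 3% |
|---|---|---|---|
| FBT only, r = 1, SD 15.3 | 0.41 | 0.76 | 1.07 |
| as % of 5.3 | 8% | 14% | 20% |
| FBT only, r = 1, SD 12.7 | 0.34 | 0.63 | 0.89 |
| as % of 5.3 | 6% | 12% | 17% |
| FBT only, r = 0.5, SD 15.3 | 0.21 | 0.38 | 0.54 |
| FBT only, r = 0.5, SD 12.7 | 0.17 | 0.31 | 0.45 |
| Same share and tail in both arms, SD 15.3 and 10.08 | 0.14 | 0.26 | 0.37 |

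The last row is (15.3 − 10.08) × the factor. With a common SD it would be zero.

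**Effect on the test at SD 15.3.** Under a normal approximation, the 0.84 entry implies SE = 5.3/(1.960 + 0.994) = 1.79. Null rejection = Φ(shift/SE − 1.96) + Φ(−shift/SE − 1.96). Power if the largest losers are removed = Φ((5.3 − shift)/SE − 1.96).

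| | 1% | 2% | 3% |
|---|---|---|---|
| Null rejection, r = 1 | 0.056 | 0.071 | 0.092 |
| Power, r = 1 | 0.78 | 0.72 | 0.65 |
| Null rejection, r = 0.5 | 0.052 | 0.055 | 0.060 |
| Power, r = 0.5 | 0.81 | 0.78 | 0.76 |

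With the t model and SE 1.59, the r = 1 results change by less than 0.01 (power 0.770, 0.709, 0.647). Both methods ignore the small fall in SD after trimming.

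**Direction.** If the largest losers are removed, the estimate moves against FBT. False rejection in favour of FBT then falls from 0.025 to 0.014, 0.009 and 0.005 (r = 1), and the inflation lies towards UC. If children with the worst outcomes are removed, for example under the illness trigger, the signs reverse and a true 5.3 would appear as 5.71, 6.06 or 6.37.

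**The case against.** The best defence is that the statistical text is specific and unqualified: all subjects are included, each with an observed, clinic-based or imputed value, and the power section plans on 24-month data for everyone. The retention clause is permissive, also covers parents and siblings, and never mentions the primary analysis. Nearby text favours keeping data: information already provided may be retained and analysed, records can be consulted after a family discontinues, and dropouts are asked for 24-month data. On this view only a clarifying sentence is missing.

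That is a reasonable prediction of what the analysts would do, and it limits the seriousness. It does not resolve the conflict: no order of precedence is stated, and permission to retain data does not cancel a separate power to remove a participant from analysis.

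The safeguards are real. Three bodies decide, one of them independent. The PIs of the Clinical Coordinating Center and the Training and Fidelity Core "and the DSMB will be masked as to treatment assignment". This lowers the risk of deliberate selection. The supplied text states no masking for the SMC and does not cover all three PIs on the SEC, but parts of the organisation section were not available and nothing here rests on that. Even a fully masked exclusion biases the comparison if the trigger is affected by treatment.

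It is also fair that every exclusion rate above is assumed, that the r = 1 rows need perfect tail removal in one arm, and that thresholds may exist in the Manual of Procedures, which was not among the documents.

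**Conclusion.** The concern holds. As written, the protocol lets index children be removed from unspecified analyses for undefined post-randomisation events, while the statistical plan requires all of them in the primary analysis.

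The likely numerical effect is modest: small unless the clause is used on more than about 1% of children and mostly in one arm. The net direction is unknown, because it depends on which trigger is used and in which arm. The size estimates rest on assumed exclusion rates, a normally distributed outcome, and r = 1 or 0.5. The textual conflict rests on none of these. It should be settled before the data are analysed, because a discretionary exclusion made after outcomes start to emerge would be hard to defend.

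**What to change.** In Participant Withdrawal or Termination, delete the reference to withdrawal from research analyses. State instead that these participants stay in the primary intention-to-treat analysis, whatever happens to their treatment, with their observed 24-month value or, if it is missing, the value obtained under section B.7. Add a cross-reference to sections A and B.7.

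If an analysis without them is wanted, add it to section E as a labelled sensitivity analysis. Fix its criteria in advance, apply them masked to arm, and report the number excluded per arm.

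The cost is one sentence of protocol wording and one optional line in the sensitivity list. Sample size, data collection, and the clinical rules on stopping treatment and referral do not change.
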